This statistical analysis plan will define and describe the analysis of the TEMP study data. The Cyprus International Institute for Environmental and Public Health of the Cyprus University of Technology is planning a randomised cross over trial of health indicators in relation to spatially varying climatic conditions ranging from the city to the mountainous environment. The purpose of the project is to understand the effect of fluctuations in external climatic conditions (e.g. air temperature) on the human body temperature and metabolic biomarkers (e.g., leptin, adiponectin, ghrelin) or stress hormones (cortisol, melatonin). The hypothesis of the project is that the number, duration and frequency of human exposures to wide gradient ($> 8^{\circ}\text{C}$) of air temperature changes, as a way of dealing with high temperatures, may be related to metabolic alterations. An intervention potentially reducing the health risk associated with extended exposure to high temperatures in the summer for Cypriots may be the temporary (for a few days) stay in the mountains of Troodos (>800 m altitude). Most of the Troodos communities have consistently lower average ambient air temperatures of $\sim 10^{\circ}\text{C}$ than those in the cities, so we hypothesize not observing the metabolic hormone alterations anticipated in the urban environment.

2 Study Design

2.1 General aspects

A 2 x 2 cross-over pilot study of healthy adults is proposed to prospectively describe the effect of ambient temperature gradient on diurnal hormonal secretion patterns. A total of 50-60 subjects will be followed for a period of 7 days firstly in an urban environment or in a village of the mountainous rural environment of Troodos and later, for the same period, in the alternate setting, during the summer period in Cyprus. The two settings will allow for the comparison of the circadian patterns of hormones secreted by the adipose tissue among different gradient temperature changes. Continuous quantification of skin temperatures on one day in each setting will allow for characterization of how skin temperature is affected by ambient temperature. Collection of all urine voids on one day in each setting will allow for quantification of the hormone secretion by the adipose tissue. In Table 1 the study characteristics of the non-pharmacological intervention are presented and in Figure 1 the order and duration of various procedures of the study are displayed.

Table 1. Study characteristics

Study Design	Randomised cross-over trial
Study groups	
Two study groups:
 
Group A: People initially staying in their permanent house in the urban area and then moving to the rural area for at least 7 days (Troodos Mountains – holiday house).
 
Group B: People initially staying in the rural mountainous area for at least 7 days (Troodos Mountains – holiday house) and then returning to their permanent house in the urban area.

Blinding	
The blinding of the participants to group assignment is not possible with the present study design. The blinding of the researchers to the subjects' identity is achieved by the coding of all study materials (urine containers, temperature sensors, questionnaires and diaries). The study personnel who will obtain the outcome measurements will be not informed of the group assignment. The personnel who will deliver the

intervention will not take any outcome measurements. All outcome assessors and data analysts will be kept masked to the allocation.

Randomisation Random allocation will be made in blocks in order to keep the sizes of treatment groups similar. Block randomisation with block size=30 and subjects no=60, will be performed using the function RAND() in Excel, that provides a random generated list, by an investigator with no clinical involvement in the trial

[figure not shown]

Figure 1. Study design

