2.5 Intervention

Table 2 presents the details of the visits and the sample collection processes.

Table 2. Visits details and sample collection process in chronological order.

Visits/Sampling days	Description
Visit 1	
The researcher visits the participant one day before the sampling day 1 (6 days after being in the urban/rural setting) and the following procedures are performed:
 
 • Administrates the consent form and receives it signed by the participant • Administrates the Questionnaire A and Chronotype Questionnaire and receives them completed by the participant • Provides coded vials for urine sampling in plastic bag and explains • Provides activity diary and explanations • Places temperature sensors on the participant (after activating them on place) and explains • Provides the instructions for urine collection and temperature sensors

	
 • Arranges appointment for the sample collection two days later (ideally in the morning)
Sampling day 1	
The participant is wearing the sensors continuously from the previous day and collects the urine voids of the day (at least 4) except for the first morning void. The participant stores the urine vials in a plastic bag in the freezer/fridge. The participant notes in the activity diary, the activities of the day (including entrance/exit from buildings, sleep/wake cycle, physical activities and meals) and their corresponding time and the times that each urine void was collected.

Visit 2	
The participant collects the first morning void of the day after the sampling day and continues wearing the temperature sensors and noting in the diary.
 
The researcher visits the participant one day after the sampling day on the arranged time and the following procedures are performed:
 
 • Collection of the urine samples and sensors • Collection and check of the completed activity diary • Sensors data are transferred immediately on a laptop, to check that data were recorded • Arrangement for the next visit that will take place in the other setting (urban/rural) with at least 2 days of washout period and on the 6th day in the alternate setting.

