Visit 3	
The researcher visits the participant one day before the sampling day 2 (6 days after being in the urban/rural setting) and the following procedures are performed:
 
 • Provides coded vials for urine sampling in plastic bag and explains • Provides activity diary and explains • Places temperature sensors on the participant (after activating them on place) and explains • Provides the instructions for urine collection and temperature sensors

	
 • Arranges appointment for the sample collection two days later (ideally in the morning)
Sampling day 2	
The participant is wearing the sensors continuously from the previous day and collects the urine voids of the day (at least 4) except for the first morning void. The participant stores the urine vials in a plastic bag in the freezer/fridge. The participant notes in the activity diary, the activities of the day (including entrance/exit from buildings, sleep/wake cycle, physical activities and meals) and their corresponding time and the times that each urine void was collected.

Visit 4	
The participant collects the first morning void of the day after the sampling day and continues wearing the temperature sensors and noting in the diary.
 
The researcher visits the participant one day after the sampling day on the arranged time and the following procedures are performed:
 
 • Collection of the urine samples and sensors • Collection and check of the completed activity diary • Sensors data are transferred immediately on a laptop, to check that data were recorded

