3.1 Timing of Analysis

The final analysis will be performed after all urine samples and temperature data are collected from all participants and 'Data and Recruitment Form' is completed.

TEMP Study

Also, the final analysis will be performed on data transferred to the file 'Full Data'. This file will be the merge of the files 'Questionnaires', 'Urine Analysis Data' and 'Temperature Data':

- **Questionnaires:** answers from questionnaire A (baseline characteristics), Chronotype questionnaire and diaries.
- **Urine Analysis Data:** data on adipokines (ghrelin, adiponectin and leptin), cortisol, melatonin and other metabolites concentrations.
- **Temperature Data:** data on ambient air and skin temperature.

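### The claimed masking of data analysts cannot hold once hormone results are merged with ambient temperature and diaries, and the masking status of the visiting researcher is left undefined

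*SAP*

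**What the plan says.** **Masking claim.** The Blinding row of Table 1 (section 2.1) concedes that participants cannot be blinded, then makes three statements about staff. On measurement staff: "The study personnel who will obtain the outcome measurements will be not informed of the group assignment". On those delivering the intervention, it says that personnel who deliver the "intervention will not take any outcome measurements". Overall: "All outcome assessors and data analysts will be kept masked to the allocation". The only device it describes is coding: "The blinding of the researchers to the subjects' identity is achieved by the coding of all study materials".

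**Field visits.** Table 2 (section 2.5) begins: "The researcher visits the participant one day before the sampling day 1 (6 days after being in the urban/rural setting". At that visit the researcher "Places temperature sensors on the participant (after activating them on place) and explains". The visit after the sampling day includes "Collection of the urine samples and sensors", a check of the diary, a download of the sensor data, and the appointment for the next visit in the other setting.

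**Analysis file.** Section 3.1 bases the final analysis on a file called Full Data: "This file will be the merge of the files 'Questionnaires', 'Urine Analysis Data' and 'Temperature Data". The Questionnaires file contains the diaries, and the Temperature Data file contains ambient and skin temperature. The introduction expects Troodos to be about 10 °C cooler than the cities.

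**Outcomes.** Section 2.8 names the hormones as primary outcomes. Table 3 (section 3.7) lists temperature as an exposure.

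**The concern.** Masking analysts protects the choices that a plan leaves open. Here, section 3.2 excludes participants whose sleep or meals departed substantially from a regular pattern, with no threshold, and section 2.3 uses the diaries and chronotype questionnaire in a similar way. Section 3.4 makes log-transformation depend on non-normality without naming a test. If such choices are made with hormone values and setting visible together, they can drift towards a difference, and nobody could tell afterwards. A reader of Table 1 would assume that this risk had been removed. The SAP's own data flow suggests that it has not, at least for analysts.

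**Working it through.** The SAP states no figure on masking, so there is none to reproduce. The check sets out who sees what, followed by one illustrative calculation.

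**1. What coding achieves.** Its stated purpose is to hide who the participant is. Hiding identity does not hide setting, period or sequence.

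**2. Role by role.**

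| Role | What the SAP lets them see | Can they be masked? |
|---|---|---|
| Participant | Own location | No (the SAP says so) |
| Visiting researcher | The setting at Visit 1; arranges the visit in the other setting | No; whether this is measurement staff is not stated |
| Laboratory staff | Coded vials | Plausible, if the code hides setting and period; not described |
| Analyst of Full Data | Hormones, ambient and skin temperature, diaries | Not in practice |

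In a two-period crossover, the setting in one period fixes the sequence. The visiting researcher therefore knows the allocation from Visit 1, and an analyst who can infer the setting of either sampling day also knows it.

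**3. What is absent.** The SAP gives no neutral code for setting, no rule keeping temperature apart from outcomes, and no time of unmasking. The primary model in section 3.9.3 names its term as rural versus urban.

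**4. How far coded labels would help.**

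Inputs:
- mean ambient difference between settings: 10 °C (SAP introduction, approximate);
- SD of a participant-day's mean ambient temperature within a setting: not in the SAP, **assumed** 2 to 6 °C;
- day means assumed normal and independent;
- 57 participants (section 2.9), used only to express the result as a count.

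Rule: call the cooler of a participant's two sampling days rural.

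P(correct) = Φ(10 / (SD × √2))

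| Assumed SD (°C) | 10/(SD√2) | P(correct) | Expected wrong out of 57 |
|---|---|---|---|
| 2 | 3.54 | 99.98% | 0.01 |
| 3 | 2.36 | 99.1% | 0.5 |
| 4 | 1.77 | 96.2% | 2.2 |
| 5 | 1.41 | 92.1% | 4.5 |
| 6 | 1.18 | 88.1% | 6.8 |

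Only the ratio of the difference to the SD matters. Halving the difference to 5 °C has the same effect as doubling the SD, so a 5 °C difference with an SD of 3 °C again gives 88.1%. Temperature alone therefore reveals setting for most participants across this range, and the diaries add further clues.

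**The case against.** The strongest reply is that masking matters most where the outcome is measured. The outcomes are objective urine assays, run on vials from coded containers, and nothing shows that laboratory staff learn the setting. This stands. A reader might infer that the trial has no masking at all, but the SAP does not support that.

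A reader might also infer that the visiting researcher is an unmasked outcome assessor, in direct contradiction of Table 1. The SAP does not establish this. Participants collect and store their own urine, the sensors record an exposure, and Table 1 separates delivery from measurement. The gap is that the visitor is assigned to neither side.

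Third, the open discretion is smaller than it may look. Non-detect handling follows fixed 20% and 70% cut-offs (section 3.6), log-transformation has a stated though loose trigger (section 3.4), and rhythm is to be tested using class means (section 3.9.1). The undefined sleep and meal exclusion is the clear exception. The SAP does not say who decides it or from which file, so one cannot assert that unmasked staff decide it with hormone results in hand. The diary check at the visit takes place when the urine is collected, before those samples can have been assayed.

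Finally, the percentages rest on an assumed SD and on ambient readings that reflect the outdoor difference. The SAP does not say whether they are outdoor or personal readings. Personal readings, with air conditioning and time indoors, could narrow the difference. The percentages also measure how easily the setting can be guessed, which is not a bias in any hormone estimate. All of this stands, but none of it rescues the statement that analysts of the merged file are masked.

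**Conclusion.** The concern holds in a limited form. Table 1 claims masking for all outcome assessors and analysts. The merged file is incompatible with that claim for analysts, and the visit procedures rule out masking of the visiting researcher, whose role the SAP leaves undefined. Assay-stage masking remains plausible but is not described.

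If labels were coded, setting could still be identified for about 88% to over 99% of participants from their two days. This assumes a 10 °C difference, independent normal day means and an SD of 6 down to 2 °C. The size of any bias in the hormone comparisons cannot be computed from the SAP, and bias through field collection of objectively assayed samples is likely to be limited. What is at stake is a protection that readers will credit but the data flow does not deliver, chiefly for the undefined sleep and meal exclusion. It should be corrected, and doing so is nearly free.

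**What to change.** **Table 1 (section 2.1).** Claim masking only for laboratory staff assaying coded vials, and state that the vial code reveals neither setting nor period. List participants, visiting researchers and analysts of the merged file as not masked. This also settles where the visiting researcher stands.

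**Section 3.1.** Before the three files are merged, require that:

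1. exclusions for irregular sleep or meals and for protocol deviations (section 3.2) are decided and locked from the Questionnaires file, without access to hormone results;
2. the transformation decision is made and locked on the Urine Analysis Data with setting, date and temperature removed.

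Only then create Full Data.

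**Cost and limits.** The three files already exist separately, so the change is wording plus a fixed order of handling. The stated masking becomes less favourable. Because the Questionnaires file includes the diaries, step 1 keeps exclusions blind to hormone results but not necessarily to setting. It also does not define what counts as a substantial departure in sleep or meals; that still needs a threshold.

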2.2 Study Objectives

Primary Objectives:

1. To investigate the effect of skin temperature gradient on the diurnal variation of adipokines and stress hormones in the two settings (urban and rural). (Null hypothesis: There is no association of skin temperature gradient with adipokine secretion.)
2. To investigate the circadian patterns of adipokines (leptin, adiponectin, and ghrelin hormones), cortisol, and melatonin in healthy individuals residing in two different climatological environments: urban and higher in latitude rural. (Null hypothesis: There is no difference in the circadian rhythm of the metabolic hormones between participants at the urban or rural environments.)

Secondary Objective:

1. To examine metabolite differences in the metabolomics-based profiles of healthy individuals with non-obese body weight in two study settings with distinctly different climatological characteristics.

2.3 Inclusion and Exclusion Criteria

Inclusion criteria	Exclusion criteria
Healthy adults between 20-60 years old	Pregnant women and obese individuals ($>30 \text{ kg m}^{-2}$)
Those that intend staying in Troodos area for the period of at least 7 consecutive days between July - September 2018.	People with chronic conditions (hypertension, diabetes, metabolic syndrome, cancer). People receiving pharmaceutical treatment for impaired glucose levels or hypertension or antidepressants or thyroxin for thyroid disorders.
	Those that have traveled to another country within the past week of the study initiation.

Eligibility will be checked through telephone communications with questions that the researcher will make to those volunteers interested for the study. People who do not meet the criteria as stated in the protocol will be excluded from the study if they are younger or older than 20-60 years old, but they won't spend summer holidays there, they are planning to travel to another country during the study period, they are obese or suffer from a particular health problem or are pregnant women.

Based on Questionnaire A, eligibility will be confirmed for those that did not answer. Volunteers that are obese or suffer from a particular health problem or they take a particular medication or they travelled to another country within the past week of the study start date, will be excluded. In the questionnaire, the variables 'BMI', 'Travel' and 'Health' will be filled with $>30 \text{ kg m}^{-2}$, tick on 'Yes' and specific country and tick on any of 'Diabetes TII / Kidney Disease / Liver Disease / Cardiovascular Disease / Respiratory System Disease / Specified Cancer / Specified Other'.

Diaries and Chronotype Questionnaires with irregular meal intakes and sleep/wake cycles will serve as another criterion to exclude volunteers from the study.

2.4 Recruitment process

Information about the study will be disseminated through flyers and through telephone communication via governmental and other non-profitable organizations (Troodos Development Company, Troodos Tourist Board, etc.) that will contact community leaders of the area and help us collect and create a contact list of “Potential Participants”. This contacts’ list will include names and phone numbers of citizens residing in one of the towns of Cyprus and who visit their house in Troodos Mountain during summer holidays. Using this list, potential participants will be informed about the study and screened for eligibility criteria via telephone.

2.5 Intervention

Table 2 presents the details of the visits and the sample collection processes.

Table 2. Visits details and sample collection process in chronological order.

Visits/Sampling days	Description
Visit 1	
The researcher visits the participant one day before the sampling day 1 (6 days after being in the urban/rural setting) and the following procedures are performed:
 
 • Administrates the consent form and receives it signed by the participant • Administrates the Questionnaire A and Chronotype Questionnaire and receives them completed by the participant • Provides coded vials for urine sampling in plastic bag and explains • Provides activity diary and explanations • Places temperature sensors on the participant (after activating them on place) and explains • Provides the instructions for urine collection and temperature sensors

	
 • Arranges appointment for the sample collection two days later (ideally in the morning)
Sampling day 1	
The participant is wearing the sensors continuously from the previous day and collects the urine voids of the day (at least 4) except for the first morning void. The participant stores the urine vials in a plastic bag in the freezer/fridge. The participant notes in the activity diary, the activities of the day (including entrance/exit from buildings, sleep/wake cycle, physical activities and meals) and their corresponding time and the times that each urine void was collected.

Visit 2	
The participant collects the first morning void of the day after the sampling day and continues wearing the temperature sensors and noting in the diary.
 
The researcher visits the participant one day after the sampling day on the arranged time and the following procedures are performed:
 
 • Collection of the urine samples and sensors • Collection and check of the completed activity diary • Sensors data are transferred immediately on a laptop, to check that data were recorded • Arrangement for the next visit that will take place in the other setting (urban/rural) with at least 2 days of washout period and on the 6th day in the alternate setting.
Visit 3	
The researcher visits the participant one day before the sampling day 2 (6 days after being in the urban/rural setting) and the following procedures are performed:
 
 • Provides coded vials for urine sampling in plastic bag and explains • Provides activity diary and explains • Places temperature sensors on the participant (after activating them on place) and explains • Provides the instructions for urine collection and temperature sensors

	
 • Arranges appointment for the sample collection two days later (ideally in the morning)
Sampling day 2	
The participant is wearing the sensors continuously from the previous day and collects the urine voids of the day (at least 4) except for the first morning void. The participant stores the urine vials in a plastic bag in the freezer/fridge. The participant notes in the activity diary, the activities of the day (including entrance/exit from buildings, sleep/wake cycle, physical activities and meals) and their corresponding time and the times that each urine void was collected.

Visit 4	
The participant collects the first morning void of the day after the sampling day and continues wearing the temperature sensors and noting in the diary.
 
The researcher visits the participant one day after the sampling day on the arranged time and the following procedures are performed:
 
 • Collection of the urine samples and sensors • Collection and check of the completed activity diary • Sensors data are transferred immediately on a laptop, to check that data were recorded

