3.8 Baseline characteristics

The baseline characteristics (recorded through questionnaire A (Table 3)) will be summarized overall and by study group. Continuous variables will be checked for normality with QQ plots and histograms. Categorical variables will be described with frequencies and percentages, normally-distributed continuous variables with means and standard deviations, and non-normal continuous variables with medians and interquartile ranges (25th-75th percentiles).

Baseline data will be tested for difference between both study groups by

- Chi-squared test for categorical variables

TEMP Study

- T-test for normally distributed continuous variables
- Wilcoxon test for non-normally distributed continuous variables

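### Consent, Questionnaire A and the Chronotype Questionnaire all fall on day 6 of the first allocated setting, so avoidable refusals and exclusions can occur after allocation

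*SAP*

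**What the plan says.** Table 2 in SAP 2.5 is set out in time order and begins with Visit 1, one day before the first sampling day and "6 days after being in the urban/rural setting". At that visit the researcher "Administrates the consent form and receives it signed by the participant" and also "Administrates the Questionnaire A and Chronotype Questionnaire and receives them completed by the participant".

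Section 2.3 describes an earlier step: "Eligibility will be checked through telephone communications with questions that the researcher will make to those volunteers interested for the study". It then turns to the form from Visit 1: "Based on Questionnaire A, eligibility will be confirmed for those that did not answer". The next sentence begins "Volunteers that are obese or suffer from a particular health problem or they take a particular medication", adds recent travel abroad, and says that such people will be excluded. Section 2.3 also excludes on irregular meals or sleep shown in the diaries and the Chronotype Questionnaire.

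Table 1 (section 2.1) defines Group A as urban first and Group B as rural first, and describes block randomisation for 60 subjects. It does not say when randomisation takes place. Section 3.2 lists everyone randomised as part of the Full Analysis population. Section 3.8 states: "The baseline characteristics (recorded through questionnaire A (Table 3)) will be summarized overall and by study group".

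**The concern.** Eligibility should be settled and consent given before a person is allocated. Here both are completed after the person has lived for six days in the setting that the allocation determines.

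Three things are at stake:

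- **The randomised set.** Someone who declines consent at Visit 1 has been allocated but provides no usable data, while section 3.2 counts all randomised subjects in the Full Analysis population.
- **Comparability of the sequences.** At Visit 1, Group A has spent six days at home in the city and Group B six days in a holiday house. Willingness to continue, and answers on which people are excluded, could differ between the two.
- **The meaning of baseline.** Questionnaire A items that respond to the current setting are not pre-intervention values, yet 3.8 tests them between groups.

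**Working it through.** **1. Order of events.** The group determines the first setting (Table 1). Visit 1 takes place six days into that setting (Table 2). Consent and both questionnaires are completed at Visit 1. The order is therefore telephone screen, allocation, six-day stay, then consent and forms. The position of allocation is inferred, but no other order is possible if the allocated group decides where the first stay takes place.

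**2. What the telephone screen leaves open.**

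| Item in section 2.3 | Listed for telephone screen | Listed for Questionnaire A |
|---|---|---|
| Age, intended stay, pregnancy | yes | no |
| Obesity, health problem | yes | yes |
| Planned travel in the study period | yes | no |
| Medication | no | yes |
| Travel in the week before the start | no | yes |

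Medication and past-week travel are listed only for the later step. Irregular sleep is judged from the Chronotype Questionnaire (Visit 1) and the diary (after Visit 1). Of these, only the diary needs to come after allocation.

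**3. Route to bias.** Let T be the true rural-minus-urban effect and P the period effect (second minus first). Group A goes to the rural setting second, so its mean within-person difference is T + P. Group B goes there first, so its mean is T − P. For complete pairs and a model with treatment only, as in 3.9.3, the pooled estimate is

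T + P × (nA − nB)/(nA + nB).

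With equal sequences the second term is zero. As an illustration only, 30 against 24 gives (30 − 24)/54 = 0.11, so 11% of any period effect enters the estimate. If P is zero, unequal loss adds nothing by this route.

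**4. Baseline items.** Section 3.8 covers Questionnaire A variables. Age, education, BMI and smoking history barely change in six days. Exercise, alcohol and screen hours could reflect the current setting.

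**5. Power.** Inputs from SAP 2.9: within-subject SD 3.53 ppb (the female value), difference 1.9 ppb, two-sided 5%, power 80%.

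- SD of the paired difference: √2 × 3.53 = 4.99.
- Normal approximation: n = 2 × [3.53 × (1.96 + 0.84)/1.9]² = 54.2, so 55.
- Exact paired t, noncentrality 1.9 × √n / 4.99 on n − 1 degrees of freedom: n = 56 gives 79.9% and n = 57 gives 80.6%. The plan's 57 is reproduced. No allowance for loss is stated.

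The SAP gives no exclusion rate, so these rates are assumptions (remaining n rounded down):

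| Assumed loss | From 60 | Power | From 57 | Power |
|---|---|---|---|---|
| 5% | 57 | 80.6% | 54 | 78.4% |
| 10% | 54 | 78.4% | 51 | 76.0% |
| 20% | 48 | 73.3% | 45 | 70.4% |

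**The case against.** The strongest reply is that the SAP never states that allocation precedes consent, that enrolment order normally belongs to the protocol (not available here), and that the telephone screen leaves Questionnaire A mainly as a confirmation for people whose answers were missing. Part of this stands: late exclusions are likely to be few. But Table 2 fixes the timing of consent itself, and the sentence after the one on missing answers excludes any volunteer on the form's content. If the protocol places consent earlier, Table 2 needs correcting.

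The consent point also carries limited weight. The stays are in participants' own houses, a Troodos stay was already intended, and Table 2 shows no sampling or sensor use before consent.

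A reader might infer more than the SAP supports:

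- *That the randomised set is lost.* It is not. A list for 60 exists, so those who refuse can be counted, though not analysed.
- *That late loss in itself biases the result.* Each completer contributes both settings, so the main route is the one in step 3.
- *That sleep timing distorts the comparison in 3.8.* That section is limited to Questionnaire A, and Table 3 lists sleep/wake cycles under the separate chronotype file.
- *That the baseline issue affects the primary estimate.* Section 3.9.3 enters no baseline covariate. The wording of the questions is not shown either, and they may ask about usual habits.
- *That a power shortfall is established.* It depends on an assumed rate; at 5% from 60 the target is still met.

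**Conclusion.** The point holds as a matter of ordering. The plan's own schedule puts consent and two eligibility forms after allocation, and so permits refusals and exclusions that could have been settled beforehand and that may differ by sequence. This rests on one inference, that allocation precedes the first stay, which the definition of the groups makes necessary.

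The statistical size is modest and uncertain. Bias needs both unequal sequences and a period effect. The power cost is about 2 percentage points below the 80.6% at 57 if 10% of 60 are lost, and about 7 points if 20% are lost. Some of any such loss would come from diaries and would remain. The baseline problem is confined to a few items. The case for change is mainly that the flaw is avoidable and that the repair is cheap.

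**What to change.** - Obtain signed consent and complete Questionnaire A and the Chronotype Questionnaire before allocation, at screening, by post or online.
- State when randomisation occurs, and randomise only people confirmed eligible.
- Near the study start, recheck only travel in the past week, since an earlier form cannot confirm it.
- Report refusals and exclusions after allocation by sequence, with reasons.
- Limit Visit 1 to sensors, vials, diary and instructions.

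If the order cannot be changed, label the setting-sensitive Questionnaire A items in 3.8 as recorded on day 6 of the first setting.

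The cost is the logistics of remote consent or an earlier contact, one repeated question and amended wording. The forms already exist. Exclusions based on diaries will still follow allocation and should be counted in the same report.
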